5.9 FOLLOW-UP AFTER END-OF-TREATMENT VISIT

Patients who finish treatment without radiological disease progression will be followed every eight weeks (\pm two weeks) from randomization until disease progression or start of a new antitumor therapy, death or until the date of study termination (clinical cutoff), whichever occurs first. Radiological tumor assessments and a tumor marker (CA-125) evaluation (if baseline levels were higher than normal) will be conducted during each of these follow-up visits. After radiological disease progression is documented or a new antitumor therapy is started, patients will be followed at least every three months (\pm two weeks) until death or date of study termination, whichever occurs first. Once the whole recruitment is completed, the 3-month follow-up for patients who discontinue treatment due to disease progression will be performed according to a calendar time. In this survival follow-up, for the purpose of collecting information, a documented telephone call would be acceptable.

The end-of-study date (clinical cutoff) is defined as 24 months after randomization of the last patient. The date and reason of the study discontinuation will be recorded on the patient's CRF (see Section [5.2.1.1](#)).

All AEs suspected to be related to the study treatment must be followed after the end of treatment until the event or its sequelae resolve or stabilize at a level acceptable to the Investigator.

Additional parameters and/or increased frequency of observations should be performed at the Investigator's discretion and according to the nature of the observed AEs. In case of death, autopsy data should be provided when available.

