Overall survival (OS) is defined as the time from the date of randomization to the date of death (death event) or last contact (in this case, survival will be censored on that date). If applicable and more than one OS analysis is performed type I error will be controlled by spending function defined by O'Brien-Fleming boundaries. Counting out subsequent therapies impact, sample size is powered to detect OS differences in the 20-30% range. Final OS analysis is planned 24 months after randomization of last patient (planned end of study date).

Landmark analyses of PFS at 6/12 months by IRC/IA and OS at 12/24 months will be the Kaplan-Meier estimates of the probability of being free from progression and/or alive at these time points.

Best antitumor response by IRC/IA will be the best response obtained in any evaluation according to RECIST v.1.1.

Radiological antitumor activity will be assessed using the RECIST v. 1.1 on a set of measurable lesions identified at baseline as target lesions, and/or non-measurable lesions (if any) identified at baseline as non-target lesions and followed until disease progression (PD) by the appropriate method [computed tomography (CT) scan or magnetic resonance imaging (MRI)].

Duration of response (DR) will be calculated from the date of first documentation of response (complete or partial response, whichever comes first) to the date of documented PD or death. The censoring rules defined above for PFS will be used for duration of response.

Assessments must be done consistently in both treatment arms to ensure a symmetrical assessment of tumor response and progression. Every effort should be made to ensure

that these assessments are done on the required date. Time to n^{th} (i.e. 1, 2, 3...) disease assessment is defined as weeks between randomization and the recorded date of the n^{th} radiology assessment after randomization.

Best response according to tumor marker evaluation (CA-125) will be the best response obtained according to GCIG criteria⁽¹⁾. Irrespectively of treatment arm, tumor marker assessment will be performed symmetrically at baseline and every eight weeks from randomization until evidence of PD.

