8.6 Imputation in Incomplete Dates

Dates of certain historical or current clinical activities are key component for statistical analysis. An incomplete date results from a missing day, month or year; in that case, the missing figure can be imputed allowing for the calculation of variables, such duration and time to certain event. However, when all of them, day, month and year, are missing no imputation will be done.

Before randomization

All variables needed to summarize for example prior information (e.g. first diagnosis date) where partial information is available will be subject of imputation by means of SAS programming. If the day of a date is unknown then the imputed day will be 1, if the month is also unknown then the imputed date will 1/July. This assumption will be valid if the imputed date is earlier than the randomization date; otherwise, the imputed date will be the first day of the randomization month date (i.e. 01/Randomization month date/year).

Between treatment start and end of treatment

All date variables during treatment where information is needed and is not fully available, for example adverse events or concomitant medications, will be subject of imputation by means of SAS programming. If the day of a date is unknown then the imputed day will be 1, if the month and/or year is also unknown then the imputed date will 1/January (this assumption will be valid if the imputed date is earlier than the treatment start date; otherwise, the imputed date will be the treatment start date).

After end of treatment

A conservative approach for the variables collecting information after end of treatment where partial information is available (e.g., main time-to-event variables; PFS and OS) will be imputed by means of SAS programming. The following rules will be implemented: if the day of a date is unknown then the imputed day will be 1; if the month is also unknown, then the imputed date will be 1/July. This assumption will be valid if the imputed date occurs later than the last drug administration date; otherwise, the imputed date will be the last drug administration date plus 1 day.

If the date of subsequent therapy is incomplete (day or month is missing) and the patient had documented disease progression, the date of subsequent therapy will be imputed to the end of the month when the progression occurred. If the subsequent therapy is given before progression to the study treatment, the rules specified above will apply.

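### The SAP checks an imputed death date only against the last dose, so a partially dated death can be placed before a later contact or scan that shows the patient alive

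*SAP*

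**What the plan says.** SAP 8.6, under the post-treatment heading, calls its approach conservative and gives as its examples the "main time-to-event variables; PFS and OS". A missing day is set to the first of the month. For a missing month the text is: "if the month is also unknown, then the imputed date will be 1/July". One plausibility check follows: "This assumption will be valid if the imputed date occurs later than the last drug administration date". If the check fails, "otherwise, the imputed date will be the last drug administration date plus 1 day".

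The same section has a separate rule for an incomplete subsequent-therapy date in a patient with documented progression. If the day or the month is missing, "the date of subsequent therapy will be imputed to the end of the month when the progression occurred".

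Other sections show what is known about patients after the last dose:

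- SAP 6.1 and Protocol 7.1 schedule scans every eight weeks until progression, including after treatment stops without progression, and survival contacts at least every three months after that.
- Protocol 5.9 says of survival follow-up that "a documented telephone call would be acceptable".
- SAP 6.1 defines OS as the "time from the date of randomization to the date of death (death event) or last contact", the last contact being the censoring date.
- SAP 3.1 includes randomized but untreated patients in the ITT population.

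Neither SAP 8.8, on missing values, nor any other section compares an imputed date with the last contact, visit or scan.

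**The concern.** The rule governs events after treatment, when the last dose is usually not the latest evidence that the patient was alive. Applied as written, it can give a death date that recorded data contradict.

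It also sits badly with the OS definition. A patient contacted on 25 September and then lost is censored on 25 September. If it is later learned that she died that year, her OS ends on 1 July. Extra information has removed survival that was already documented.

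For an ITT patient who was never dosed, the lower limit does not exist.

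The subsequent-therapy rule has a related fault. When only the day is missing, it throws away a recorded month and substitutes the month of progression.

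**Working it through.** The plan gives no figure on this point, so there is none to reproduce. The check applies the rule literally.

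**Rule as written.** Imputed date = day 1 of the recorded month, or 1 July of the recorded year if the month is also missing. If that is not later than the last dose, use last dose + 1 day.

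**Illustrative cases.** In the first two, the last dose was before the imputed date.

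| Recorded death | Last dose | Last known alive | Imputed death | Days before known alive |
|---|---|---|---|---|
| September, no day | before 1 September | scan 20 September | 1 September | 20 − 1 = 19 |
| Year only | before 1 July | contact 25 September | 1 July | 30 + 31 + 25 = 86 |
| June, no day | 1 June | seen 29 June | 2 June (fallback) | 27 |
| Year only | 10 August | contact 10 December | 11 August (fallback) | 121 |

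The last two rows show that the fallback fails in the same way.

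**How often, among incomplete death dates.** The documents give no timing data, so these are assumptions: deaths spread evenly over the calendar; last dose 30 to 400 days before death; last contact alive 1 to 56 days before death (scan interval) or 1 to 91 days (three-monthly contact). The rule, including its fallback, was applied to 200,000 simulated deaths for each interval.

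| Missing | Contact interval | Imputed on or before last known alive | Mean days before, in those cases | Maximum | Mean error against true date, all cases |
|---|---|---|---|---|---|
| Day | 91 days | 16.2% | 9.5 | 29 | −14.7 days |
| Day | 56 days | 26.3% | 9.5 | 29 | −14.8 days |
| Day and month | 91 days | 36.0% | 62.8 | 182 | +3.4 days |
| Day and month | 56 days | 41.9% | 68.5 | 182 | +3.7 days |

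The percentages include ties. A death on the day of last contact is possible; without ties, 16.2% becomes 15.1%.

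**What a last-known-alive limit does.** It moves each affected date to the day after last known alive, so the mean error changes by (share affected) × (mean days before + 1). With 91-day contacts:

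- Day missing: −14.7 + 0.162 × 10.5 = −13.0 days.
- Day and month missing: +3.4 + 0.360 × 63.8 = +26.4 days.

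The limit removes the contradictions. It does not make the imputation unbiased: day-missing deaths are still dated early on average, and with only the year known the dates that are too late are no longer offset by dates that are too early.

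**Subsequent therapy.** Take a last infusion on 10 August, progression in August, and new therapy recorded as October without a day. The rule dates the therapy 31 August. SAP 8.3 ends time on treatment at new therapy if it starts within 30 days of the last infusion. It therefore stops at 21 days after that infusion, on 31 August, instead of 30 days, on 9 September. The recorded month shows that therapy had not started by then.

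**The case against.** Several objections carry weight.

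- **Partial dates may be rare.** Protocol 7.1 and SAP 6.1 require the date of death to be registered and documented, survival calls go to the sites, and the listings in SAP Section 13 show a death report form with a date field. No document gives a rate of partial dates. The percentages above are shares of an unknown, possibly very small, number. This stands.
- **PFS is less exposed than the SAP wording suggests.** The IRC assigns progression and censoring dates, and PFS is censored at a tumor assessment. The fault reaches PFS where a partially dated death is itself the PFS event. This stands.
- **The rule is the same in both arms.** A reader might infer that it biases the treatment comparison. The documents do not support that: nothing in them says which arm would have more partial dates.
- **Safety data.** A reader might infer that the subsequent-therapy rule cuts adverse-event collection short. Protocol 7.4.1 ties collection to the actual start of new therapy, and no section says that events after an imputed therapy date are dropped. The derived variable clearly affected is time on treatment.
- **Data queries could catch such cases.** They might, but neither document specifies a check, and SAP 8.6 says the imputation is done by programming.

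None of this supplies the missing lower limit.

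**Conclusion.** The point holds as a fault in a stated rule. Followed literally, SAP 8.6 can end OS before documented survival, by 19 and 86 days in the two simple examples. It can do the same to PFS where the death is the PFS event. Under the stated timing assumptions this happens to about 16% to 26% of day-missing deaths and 36% to 42% of deaths known only by year.

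The number of such deaths is unknown and the effect on the hazard ratio is probably small. The conservative label is not established: day-missing deaths move about 15 days earlier on average, year-only deaths show almost no average shift, and neither error is shown to favor control. A reader should not conclude that the primary result is unreliable; the documents do not support that. The case for acting is that the rule contradicts recorded data and is easy to correct before analysis.

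**What to change.** 1. **Death dates.** Keep the day 1 and 1 July rules. Set the imputed death date to the later of the rule date and the last date documented alive plus one day, held within the recorded month or year. The last date documented alive is the latest contact, visit, tumor assessment, laboratory test or dose, or the randomization date for an untreated patient with nothing later. In the two simple examples this gives 21 September and 26 September.
2. **Subsequent therapy after progression, only the day missing.** Keep the recorded month and use the later of its first day and the progression date plus one day. Use the month of progression only when the therapy month is unknown. In the example, therapy is dated 1 October and time on treatment runs its full 30 days.
3. **Wording.** Remove the word conservative, or say in what sense it is meant.

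The cost is SAP text and a few lines of SAS. The dates needed are already collected, and no clinical procedure changes.

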7 STATISTICAL METHODOLOGY FOR SAFETY

7.1 *Toxicity and Adverse Events*

Patients will be evaluable for safety if they have received any partial or complete treatment infusion. All AEs will be graded according to the NCI-CTCAE v.4. Treatment delays, dose reduction requirements and reason for treatment discontinuation will be monitored throughout the study.

The safety profile of patients will be monitored throughout the treatment and up to 30 days after the last treatment infusion (end of treatment, EOT), or until the patient starts a new antitumor therapy or until the date of death, whichever occurs first.

Any AEs will be coded using to the Medical Dictionary for Regulatory Activities (MedDRA). Treatment-related AEs will be followed, whenever possible, until recovery to at least grade 1 or stabilization of symptoms, whenever possible.

Summary of overall AEs will be done by body system and preferred term, by severity (worst toxicity grade) and by relationship. Tables will be sorted by body system/preferred term.

A frequency table will be made for the AEs leading to cycle delay, dose reduction, skipped dose (topotecan only), or withdrawal of study medication. AEs leading to permanent treatment stop and AEs with outcome of death will also be presented by relationship to drug.

Exploratory Fisher's exact tests will be performed to compare the incidence of grade 4 or grade 3/4 AEs between treatment arms.

7.2 *Clinical Laboratory Evaluation*

Laboratory results will be classified according to the NCI-CTCAE v.4.

The worst grade per patient will be tabulated during overall treatment and per cycle for hematology values [white blood cells (WBC), absolute neutrophil count (ANC), lymphocyte count, platelet count and hemoglobin] and for the following biochemistry tests: alanine aminotransferase (ALT), aspartate aminotransferase (AST), total bilirubin, alkaline phosphatase (AP), creatine phosphokinase (CPK), creatinine, glucose, sodium, potassium and albumin.

Exploratory Fisher's exact tests will be performed to compare the incidence of grade 4 or grade 3/4 laboratory evaluations between treatment arms.

7.3 *Physical Examination Findings*

Tables summarizing the performance status (PS), height, body weight and BSA (according to the Dubois and Dubois formula) at baseline will be prepared.

In addition, changes in the ECOG PS and body weight of each patient during the treatment compared to baseline will be presented.

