8.3 Treatment Administration

Total cumulative dose, time on treatment, dose intensity and relative dose intensity, administration delay, and dose reductions/omissions will be described following standard tables (detailed in Appendix I) and the reported cycle information on the case report form (CRF) pages will be used for the analyses.

Total cumulative dose by drug, expressed in mg, is the sum of all the product doses from the first cycle until the last cycle, including the dose received in the last cycle.

Time on treatment, expressed in weeks, is defined as last infusion date minus first infusion date plus 30 days, except if the patient dies or starts a new antitumor therapy within 30 days from the last infusion date, in which case the time on treatment will be the date of death or the date of the start of a new antitumor therapy minus the date of the first infusion.

Intended dose intensity is the planned dose per cycle divided by the planned number of weeks by cycle.

Absolute dose intensity is the actual cumulative dose divided by the number of weeks of treatment. As a convention, for this calculation, the duration of the last cycle will be the predefined cycle length (i.e., 21 days or 28 days in case of PLD). Relative dose intensity (%) is the ratio of absolute dose intensity divided by the intended dose intensity.

The items « Infusion delayed: yes/no» and « Dose reduced: yes/no» present on the drug

administration CRF page will be used to calculate delays and dose reductions, respectively. For cycles considered as delayed by the Investigator, the length of the delay will be calculated as:

Duration of cycle delay: Date of the current drug administration – Date of the previous drug administration – the predefined cycle length (i.e., 21 days if PM01183/topotecan or 28 days if PLD).

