8.5 Subsequent Therapies

A table summarizing the subsequent therapies received after discontinuation will be shown. Special attention will be focused on patients receiving any platinum compound as first subsequent treatment, and analyses to test between treatment arms if potential platinum-free interval prolongation is associated with survival.

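### SAP 8.6 overwrites a reported month: any incomplete subsequent-therapy date after progression is moved to the end of the progression month, with no floor at the last infusion

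*SAP*

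**What the plan says.** SAP 8.6 treats post-treatment dates in two steps. The general rule keeps what the site reported. Its convention for an unknown day is the one used throughout the section: "If the day of a date is unknown then the imputed day will be 1". If the imputed date does not fall after the last dose, a floor applies: "otherwise, the imputed date will be the last drug administration date plus 1 day".

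A separate paragraph then covers subsequent therapy. Its trigger is: "If the date of subsequent therapy is incomplete (day or month is missing) and the patient had documented disease progression". In that case "the date of subsequent therapy will be imputed to the end of the month when the progression occurred". The one exception is: "If the subsequent therapy is given before progression to the study treatment, the rules specified above will apply". The paragraph says nothing about using a reported month, does not repeat the floor, and does not say whether progression is by the investigator or by the independent review committee (IRC).

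The start of new therapy is used elsewhere. In SAP 8.3, time on treatment is last infusion minus first infusion plus 30 days, unless the patient dies or "starts a new antitumor therapy within 30 days from the last infusion date". SAP 7.1 follows safety to 30 days after the last infusion "or until the patient starts a new antitumor therapy or until the date of death, whichever occurs first". Protocol 5.2.1.1 makes the new-therapy date the end-of-treatment (EOT) date when it comes first.

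**The concern.** SAP 8.6 opens by describing imputation of the part of a date that is missing. The subsequent-therapy rule goes further. When only the day is missing, it also replaces the month, which is known, and can give a date that contradicts the source record.

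At stake are derived quantities that depend on when new therapy began: time on treatment, the EOT date, and the on-treatment window after the last infusion. A start that is falsely early can cut all three. Without the floor, new therapy can even be dated before the last study dose.

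**Working it through.** The SAP states no figure on this point, so there is none to reproduce. The check applies the rule literally to example dates.

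**Inputs.** The trigger, the imputed value and the general rule come from SAP 8.6. The 30-day window comes from SAP 7.1 and 8.3. The documents give neither the gap from last infusion to progression nor the gap from progression to next therapy, so the dates below are assumptions.

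**Formulas.** Let I be the last infusion and M the last day of the progression month.

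- Imputed start = M.
- Back-dating = (first to last day of the reported month) minus M.
- Window after last infusion = min(30, imputed start minus I).

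**Back-dating.** For progression in March, M = 31 March.

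- Reported as unknown day in June: 31 March to 1 June = 30 + 31 + 1 = 62 days; to 30 June = 62 + 29 = 91 days.
- Reported as unknown day in April: 1 to 30 days early.

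**Window.**

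| Last infusion | Progression | Therapy reported in | Window, rule as written | Window, reported month with day 1 |
|---|---|---|---|---|
| 10 March | 20 March | June | 31 − 10 = 21 days | 30 days |
| 22 March | 25 March | June | 31 − 22 = 9 days | 30 days |
| 1 March | 3 March | June | 30 days | 30 days |
| 10 March | 20 March | April | 21 days | 22 days |
| 5 April | 28 March | June | start 5 days before last infusion | 30 days |

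The loss is 9 days in the first row, 21 in the second and none in the third. The last row shows the effect of the missing floor; it needs a progression date earlier than the last dose, for example an IRC date that precedes the investigator's.

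**How the cut depends on the unstated gap.** Suppose the true start is more than 30 days after the last infusion. The loss is then max(0, 30 − (M − I)). Taking progression on each day of a 365-day year:

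| Assumed gap, last infusion to progression | Share of affected patients with a cut window | Largest loss |
|---|---|---|
| 0 days | 98% | 30 days |
| 7 days | 76% | 23 days |
| 14 days | 53% | 16 days |
| 21 days | 30% | 9 days |
| 28 days | 7% | 2 days |

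The base for these shares is progressed patients with an incomplete therapy date, not all patients.

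**Where the rule works.** Take last infusion 10 March, progression 20 March, and therapy reported as an unknown day in March. The general rule gives 1 March, which its floor moves to 11 March, still before progression. The special rule gives 31 March. If therapy followed progression, that is at most 31 − 20 = 11 days late and never early.

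**The case against.** The strongest defence is that the rule has a sound purpose. As the last example shows, day 1 of the progression month can create therapy that appears to precede progression, and that is the situation in which the PFS definition censors. Month-end imputation prevents this. The defence stands for therapy reported in the progression month, and the convention is also usable when the month is missing. It does not justify replacing a later month that the site supplied.

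The consequences are also narrower than a reader might infer:

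- **Adverse events lost.** Sites collect events by real dates (protocol 5.8 and 7.4.1), and a date imputed at analysis cannot stop that. SAP 12.2.1 states no filter that removes recorded events after an imputed therapy start. Dose intensity is protected, because SAP 8.3 fixes the last cycle at its planned length.
- **Window often cut.** No figure in the documents supports a frequency. Under the assumed gaps the share runs from 98% down to 7%.
- **Platinum-free interval too short.** SAP 8.5 asks whether "potential platinum-free interval prolongation is associated with survival", but the only definition of that interval (SAP 2; protocol 1.1) ends at relapse or progression. Under it, the start of next therapy does not enter.
- **Primary endpoint distorted.** Censoring uses the last assessment before new therapy, and a month-end date does not precede the progression scan. Scheduled scans stop after radiological progression (protocol 7.1). An IRC event could be lost only if progression by the investigator alone counted as documented, the therapy date were incomplete, and a further scan between the month-end and the true start were read as progression by the IRC. That is a rare possibility.

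**Conclusion.** The point holds as a defect in a stated rule. Read literally, SAP 8.6 discards a known later month and can back-date new therapy by weeks to months: 62 to 91 days for March progression with therapy reported in June. It also has no floor at the last infusion.

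The demonstrable effect is on time on treatment, the derived EOT date and the derived on-treatment safety window, and only when the progression month ends within 30 days of the last infusion. The examples lose 9 and 21 days. If dosing stopped by the end of the progression month, the loss cannot exceed 30 days.

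The conclusion on back-dating needs only the SAP text and the calendar. The size of the window loss rests on assumed gaps. How many patients would have such dates is not given. Overall survival is unaffected, and PFS by IRC is ordinarily unaffected. The correction is worth making because the rule can contradict source data and is cheap to repair.

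**What to change.** Reword the subsequent-therapy paragraph of SAP 8.6 for patients with documented progression:

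- **Month known and later than the progression month:** keep it and impute day 1, as in the general rule, but no earlier than the day after progression or the day after the last infusion.
- **Month missing, or equal to the progression month:** use the end of the progression month, with a floor at last administration plus 1 day.
- **Therapy before progression:** leave the present exception as it is.

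The paragraph should also say whose progression date counts, the investigator's or the IRC's.

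In the first example (last infusion 10 March, progression 20 March, therapy in June) the start becomes 1 June and the window returns to 30 days. In the second (last infusion 22 March) 21 days are restored. The cost is about two sentences in SAP 8.6 and a small edit to the imputation program. No new data are needed, and the protection against false pre-progression therapy is kept.
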